6.3 Data to be collected

- Patient demographics, feeding and growth outcomes, length of hospital stay and comorbidities will be collected from parents and from medical records. Basal manometry data will be collected to assess the mechanisms of normal or abnormal swallowing. Multimodal sensory motor testing involves mid-esophageal provocation with graded infusions (0.1 to 5 ml) of air (to stimulate mechanoreceptors), apple juice (pH 3.7, to stimulate acid-sensitive receptors), and sterile water (pH 7.0, as control stimulus), and examine the changes in sensory-motor characteristics of aerodigestive reflexes. Basal and adaptive pharyngeal reflexes with air and water infusions are measured.

- 6.4 Long term follow-up will include feeding method, growth characteristics and development up to 1 year of age.

7.0 Sharing of Results with Subjects*

- 7.1 Manometry results are shared with the parents at the time of the study. Parents decide on their preferred feeding approach (flow change, thickener change, no change) and if the patient is inpatient, this is shared with the medical team.

8.0 Study Timelines*

- 8.1 Describe:

- The individual subject's participation in the study will last ≤ 4 weeks. Data will be collected for the first year of life.
- The duration anticipated to enroll all study subjects is between 2/16 until 7/20.
- The estimated date to complete this study (complete primary analyses) is 12/20.

9.0 Inclusion and Exclusion Criteria*

- 9.1 All infants < 6 months PMA who are scheduled for a VFSS will be screened for the above eligibility criteria.
- 9.2 All subjects who consent and receive a concurrent or sequential VFSS and esophageal manometry will be included in the analysis.
- 9.3 Our population will include individuals who are not yet adults (infants)

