- Three references are attached below in this section that lend support to our investigations, difficulties with strict protocols and need for personalization and parent preferred pragmatic therapies. Complimentary protocols (feeding outcomes in dysphagia, mechanisms of dysphagia, outcomes in gastrostomy bound infants) will address the original study aims as well. Updated statistical procedures based on the advice of our statistician, [name], PhD, DSMB team, and our Program Project Group is shown below.

3.3 Updated statistical procedures:

- The design of the Patient Preferred Trial has been modified to a single arm observational study with patients who have not achieved PO at the time of study or PO with feeding difficulties, comparing VFSS and manometry vs VFSS only (the historical control) on feeding outcomes. The primary outcome is success rate at discharge. We will prospectively follow 60 infants who are not fully PO or PO and symptomatic at the time of study. Based on our Feeding Outcomes of Dysphagia Study (vs. historical control), the success rate at discharge is around 60%. With 60 patients enrolled, we will have 90% power to detect an absolute increase of 20% from 60% for those who do not have treatment informed by manometry (historical control) to 80% in those in the manometry informed group with two-sided type I error of 0.05. Achievement will be assessed by tracking feeding methods at discharge or 4 weeks whichever is earlier and then at 1 year.
- [name], Peng J, Moore R, Saavedra J, Shepherd E, Fernandez S, Erdman SH, DiLorenzo C. Impact of personalized feeding program in 100 NICU infants: pathophysiology-based approach for better outcomes. *J Pediatr Gastroenterol Nutr.* 2012 Jan;54(1):62-70.
- [name], Stoner E, Gupta A, Bates DG, Fernandez S, Di Lorenzo C, Linscheid T. Evaluation and management of neonatal dysphagia: impact of pharyngoesophageal motility studies and multidisciplinary feeding strategy. *J Pediatr Gastroenterol Nutr.* 2009 Feb;48(2):186-92
- [name], Khot T, Moore R, Malkar M, Gulati IK, Slaughter JL. Feeding Methods at Discharge Predict Long-Term Feeding and Neurodevelopmental Outcomes in Preterm Infants Referred for Gastrostomy Evaluation. *J Pediatr.* 2017 Feb;181:125-130

3.4 Scientific or scholarly background for, rationale for, and significance of the research based on the existing literature and how will it add to existing knowledge

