6.0 Procedures Involved*

6.1 Study Design

- Study design and setting: Eligible subjects (study) will undergo diagnostic VFSS in combination with manometry, either concurrent or sequential. They will have parental choice of preferred feeding therapy. The data is from single center prospective observational study. The controls are those who had VFSS alone with provider recommendations from the same single center.
- Patient population and characteristics: (i) Study and control infants have oral feeding difficulties with symptoms requiring interventions/monitoring. (ii) They have diagnostic need for VFSS due to aerodigestive and feeding difficulties. (iii) Study subjects must have a signed informed consent from parent/legal guardian prior to manometry study. Control subjects did not require consent as they were historical controls.
- Inclusion criteria: Infants with feeding-related aerodigestive symptoms who are \leq 60 wks PMA (both pre-term and full-term) who are orally feeding \geq 25% of at least 50% of their feeds who are on full enteral feeds with no more than 1LPM NC respiratory support. All infants will have a diagnostic VFSS scheduled.
- Exclusion criteria: Genetic or metabolic syndromes, grade III or greater, moderate to severe HIE, craniofacial, airway or foregut malformations or ENT or neuro surgeries. Infants who are exclusively breastfeeding are also excluded.
- Test-1: VFSS with concurrent or sequential pharyngo-esophageal manometry along with standard safety metrics. Esophageal and pharyngeal provocation induced

PROTOCOL TITLE: Neonatal Esophagus and Airway Interactions in Health and Disease: Mechanisms and Management of Infant Dysphagia

aerodigestive reflexes will be tested. Oral feeding challenge test is performed during manometry. The same procedures without VFSS will be repeated at Time-2 where feasible and relevant.

- Overall Study Endpoints: Primary endpoint is therapeutic success defined as full oral feeding without symptoms requiring intervention at 4 weeks (for outpatient studies and those still admitted at 4 weeks) or discharge, whichever is earlier. Secondary clinical end points include growth velocity and feeding outcomes at 1 year.
- Methods to overcome Potential Confounders: It is NICU standard to document in EPIC: i) Daily documentation of symptoms, medication use, feeding methods and duration, feeding volume and weight, ii) Weekly documentation of growth velocity (weight, length, head circumference).

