13.0 Withdrawal of Subjects*

- 13.1 Patients will be withdrawn if there are any safety concerns with continuing.
- 13.2 If a parent decides to withdraw their infant, follow up data will continue to be collected.

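### Section 9.2 counts only consented infants who go on to receive manometry, a step the VFSS-only controls never face, and no all-consented comparison is planned

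*Combined protocol and SAP*

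**What the plan says.** The only statement of who is analysed is in 9.2: "All subjects who consent and receive a concurrent or sequential VFSS and esophageal manometry will be included in the analysis". Section 6.1 fixes the order of events for the study group: "Study subjects must have a signed informed consent from parent/legal guardian prior to manometry study". It allows manometry to be done at the same time as the VFSS or afterwards, and sets no maximum interval between the two.

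For the comparison group, 6.1 says: "The controls are those who had VFSS alone with provider recommendations from the same single center". It adds: "Control subjects did not require consent as they were historical controls".

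The outcome being compared is also in 6.1: "Primary endpoint is therapeutic success defined as full oral feeding without symptoms requiring intervention at 4 weeks", or at discharge if that comes first. Section 3.3 sizes the study on that outcome: "With 60 patients enrolled, we will have 90% power to detect an absolute increase of 20% from 60" percent, "to 80% in those in the manometry informed group with two-sided type I error of 0.05".

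On withdrawal, 13.1 says: "Patients will be withdrawn if there are any safety concerns with continuing". Section 13.2 keeps collecting follow-up data when a parent withdraws an infant. Neither clause says how withdrawn infants enter the analysis. No section assigns consented infants without manometry to any analysis, plans to count them, or provides a sensitivity analysis that includes them.

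**The concern.** A study infant reaches the denominator by passing two steps beyond the VFSS: consent, then manometry. A control needs only the VFSS. Manometry comes after consent, so the study success rate describes infants who completed a later step, and nothing in the definition of the controls selects them in the same way.

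Infants may fall out between consent and manometry for reasons related to feeding: withdrawal, a safety concern, a probe that is not tolerated, or improvement and discharge before a sequential study. If those infants differ in their chance of full oral feeding, part of the difference between study and control rates comes from who was counted. The comparison is not randomised, so it rests on the two denominators being built alike. At stake is the reading of the primary result, a rise from 60% to 80%.

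**Working it through.** **1. The plan's own figure.** Inputs from 3.3: control rate 0.60, study rate 0.80, n = 60, two-sided alpha 0.05. Treat 60% as a fixed constant.

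- Standard error under the null: √(0.6 × 0.4/60) = 0.0632. Under the alternative: √(0.8 × 0.2/60) = 0.0516.
- Power = Φ[(0.20 − 1.96 × 0.0632)/0.0516] = 93.0%. With a continuity correction of 1/120 it is 90.5%.
- Exact binomial: reject at 44 or more of 60, upper tail 0.022, power 92.3%.

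The stated 90% is reproduced as a one-sample comparison. The analysis-set question does not change it.

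**2. All-consented rate.** Assume 48/60 = 80% in the manometry set, with e further consented infants who had the VFSS but no manometry and who succeed with probability q. Both e and q are assumptions. The rate is (48 + e × q)/(60 + e).

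| e (share of consented) | q = 0 | 20% | 50% | 80% | 100% |
|---|---|---|---|---|---|
| 3 (4.8%) | 76.2% | 77.1% | 78.6% | 80.0% | 81.0% |
| 6 (9.1%) | 72.7% | 74.5% | 77.3% | 80.0% | 81.8% |
| 9 (13.0%) | 69.6% | 72.2% | 76.1% | 80.0% | 82.6% |

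For example, (48 + 6 × 0.2)/66 = 49.2/66 = 74.5%. The rate is unchanged if the omitted infants do as well as the rest, falls if they do worse, and rises if they do better.

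**3. Would the conclusion change?** Against a fixed 60%, z = (rate − 0.60)/√(0.24/N).

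- 48/60: 0.200/0.0632 = 3.16.
- Six added, all failing (48/66): 0.1273/0.0603 = 2.11, still above 1.96.
- Nine added, all failing (48/69): 0.0957/0.0590 = 1.62, below 1.96.

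With the planned 80% observed, it takes a fairly extreme loss to overturn the result. A smaller observed effect would be more fragile. Section 16.1 plans a chi-squared or Fisher test against the historical group, whose size is not given, so these z values are a guide only.

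**4. Error rate if there is no effect.** Assume the true rate among all consented infants is 60%, 60 infants are analysed, and a fraction f = 10% of the consented is left out with success q. The analysed infants then have rate (0.60 − f × q)/(1 − f). The last column is the chance of 44 or more successes in 60.

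| q among those left out | Analysed rate | Chance of declaring benefit |
|---|---|---|
| 0% | 66.7% | 0.169 |
| 20% | 64.4% | 0.094 |
| 40% | 62.2% | 0.048 |
| 60% | 60.0% | 0.022 (nominal) |
| 80% | 57.8% | 0.009 |

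**The case against.** Section 9.2 says who is included and names no exclusion, so leaving infants out is an inference. That is correct, but with no other set defined it is the natural reading, and one sentence would settle it. The rule also has a protective side: every infant who has both tests is analysed, whatever therapy or outcome follows.

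A reader might infer that safety withdrawals under 13.1 leave the analysis. The text does not support that in general: an infant withdrawn after manometry still meets 9.2. Only losses between consent and manometry matter here.

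A reader might also infer that the rule inflates the study rate. The documents do not establish a direction. Eligibility in 6.1 requires full enteral feeds, limited respiratory support and some oral feeding. Section 14.1 likens the probe risk to that of a nasogastric tube, and 10.1 describes staff who do these studies regularly. Losses through instability may therefore be few, especially when manometry is concurrent. With a sequential study, infants who improve and go home first could be missed, which would lower the study rate.

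Controls are themselves conditioned on having had a VFSS, and how that cohort was assembled is not described here. The asymmetry therefore lies in consent and manometry only.

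The strongest argument is about the question being asked. Section 3.3 contrasts a manometry-informed group with infants treated without it, and 5.1 makes manometry the intervention. An infant who never had it did not receive the intervention, and there is no randomised assignment to preserve. This stands: it is a good reason not to make the all-consented set the sole primary analysis. It is no reason to leave those infants uncounted.

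**Conclusion.** The point holds as a gap in the analysis set. The study success rate is conditioned on a post-consent step that has no counterpart in the controls, and nothing elsewhere in the plan repairs or measures this. The claim does not extend to a known inflation of the effect, because neither the number nor the outcomes of the affected infants can be found in the documents.

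Under the illustrative assumptions, six omitted infants move an observed 80% to somewhere between 72.7% and 81.8%, or about 7 points down to 2 points up against a planned 20. If there is no true effect and 10% are omitted, the chance of declaring benefit runs from 0.009 when they succeed at 80%, through the nominal 0.022, to 0.169 when they all fail. If losses are negligible, so is the effect. The stated power is untouched. This is a cheap improvement to the plan and not a fatal flaw.

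**What to change.** Amend 9.2 to prespecify two comparisons with the historical controls: the manometry-completed set as now written, and beside it an all-consented set containing every consented, eligible infant who had the diagnostic VFSS, with or without manometry. Take the discharge or 4-week feeding endpoint from the medical record and the follow-up already collected. Report how many consented infants had no manometry, with reasons. State in advance that a claim of benefit will be qualified if the two sets disagree.

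Most of the data should exist: 6.1 describes routine daily feeding documentation for NICU infants, 13.2 continues data collection after parental withdrawal, and 18.2 gives access to records. Extra review falls mainly on outpatients, for whom 6.2 also relies on diary logs. The other cost is a possibly lower success rate.

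Two limits remain. The change does not remove selection by consent itself. Section 8.1 expected enrolment to end in 7/20 and the current version is dated 10/2/20, so the amendment should state whether outcomes had been examined when it was made.

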10.0 Vulnerable Populations*

10.1 This research complies with 45 CFR 46, as it includes only human infants up to 6 months old. As this study involves slightly greater than minimal risk, as regulated in 45 CFR 46 Subpart D, all subjects for this study will have consent of at least one parent.

- The Neonatal and Infant Feeding Disorders (NIFD) Program is directed by the PI, [name] who is a Neonatologist with Pediatric GI experience and is a recognized GI motility expert. The NIFD program is a nationally recognized clinical program supported by the NIH and is well equipped to conduct clinical studies such as proposed in this application. In addition, there is a team of dedicated trained nurse coordinators who are competent and comfortable with performing these procedures on preterm infants as well as a neonatal nurse practitioner. The team also includes trained technical personnel affiliated to this program who perform these studies on a regular basis for diagnostic purposes in this same population.

11.0 Local Number of Subjects

11.1 60 subjects

12.0 Recruitment Methods

- 12.1 Parents of infants scheduled for a VFSS who meet the eligibility requirements will be approached
- 12.2 Subjects will be recruited from the VFSS schedule at NCH.
- 12.3 RN Coordinators will identify and screen potential subjects.
- 12.4 There will be a \$20 payment for each study completed.

13.0 Withdrawal of Subjects*

- 13.1 Patients will be withdrawn if there are any safety concerns with continuing.
- 13.2 If a parent decides to withdraw their infant, follow up data will continue to be collected.

14.0 Risks to Subjects*

- 14.1 This study includes the risk associated with the nasal placement of the manometry probe and the infusion catheter. These risks are similar to the risks associated with the placement of a nasogastric feeding tube in infants which is frequently done for tube feeding infants both in the hospital and sometimes at home.

15.0 Potential Benefits to Subjects*

- 15.1 The addition of the esophageal manometry to the VFSS will provide added information as to the etiology of the infants feeding problem. This can be used to improve treatment options and possibly improve outcomes.

16.0 Data Management* and Confidentiality

16.1 Data Analysis Plan

- Descriptive statistics will be reported as median (IQR), mean \pm SD or total number and percentage for demographics and clinical characteristics. For PPG vs FOD historical control comparisons, two-sample t-test or ANOVA will be used for the continuous variables and chi-squared or Fischer's exact tests will be used for the categorical variables, whichever is appropriate. Non-parametric method (e.g. Wilcoxon) might be used if the data is not normally distributed. Normality will be assessed using Shapiro-Wilks test and visually inspection of the data. For other Normal vs Abnormal VFSS and the effect of parent preferred therapy -flow modification or thickener use) comparisons, due to the nature of the repeated measure of the data, repeated measure ANOVA for continues measured variables and Generalized estimating equation (GEE) for categorical variables, to predict the likelihood of the specific response, will be used as to make the between group comparisons. Compound symmetry (CS) will be specified for the covariance structure of the repeated data. Bonferroni correction will be used to conserve the overall type I error at $\alpha=0.05$. To characterize the association between the disease comorbidities and feeding success, simple and multiple logistic regression analysis will be performed. Statistical Analysis Software, version 9.4 (SAS Institute Inc., Cary, NC, USA)

- 16.2 Data will be stored in RedCap and each subject will have a file which is kept in a secured locked location.

- 16.3 Data will be verified by at least two individuals on the study team

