2.2 Hypothesis

- The central unifying hypothesis supported by our preliminary data is that VFSS with the addition of Manometry along with parent preferred feeding strategy is more effective in preventing long term feeding tubes in infants with aerodigestive problems and feeding difficulties.
- **Primary Hypothesis:** The addition of manometry for diagnostics and parent preferred therapy for management is more effective than VFSS with provider recommendations alone for achieving primary outcome.
- **Secondary Hypotheses:** 1) The sensory- motor characteristics of pharyngo-esophageal motility markers are distinctive between normal and abnormal VFSS results. 2) Clinical outcomes are distinct with flow modification and thickener use.

3.0 .Background

3.1 Relevant prior experience and gaps in current knowledge.

- Dysphagia or abnormalities of swallowing, is a heterogeneous condition of multiple etiologies. Pharyngeal phase is the most critical phase since imprecise regulation is associated with airway consequences such as laryngeal penetration and airway aspiration. Exact prevalence is not known, but is estimated to be about 30% to 60% among neonatal ICU graduates. Although these numbers highlight the economic burden, they ignore the quality of life for both patients and parents. The lack of a pathophysiology guided diagnostic and safe feeding management strategies continue to be critical barriers to progress in this field. The current proposal focuses on the dynamic changes in the integrative physiology of the neonatal pharynx, upper esophageal sphincter (UES), lower esophageal sphincter (LES) and esophagus during swallowing and GERD; all of which are potential therapeutic targets for neonates with dysphagia. Current treatment approaches in dysphagic infants are likely to fail due to unclear therapeutic targets. Such high risk infants also suffer chronic morbidity, longer hospitalizations, re-admissions, and account for an unacceptable health care burden. Designing effective symptom-based management is very difficult.

3.2 Relevant preliminary data.

PROTOCOL TITLE: Neonatal Esophagus and Airway Interactions in Health and Disease: Mechanisms and Management of Infant Dysphagia

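### The comparison with historical controls that tests the primary hypothesis is unadjusted, and the plan does not say that the 6.1 eligibility criteria were applied to the controls

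*Combined protocol and SAP*

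**What the plan says.** Section 2.2 frames the primary hypothesis as a comparative claim: manometry for diagnosis plus "parent preferred therapy for management is more effective than VFSS with provider recommendations alone for achieving primary outcome". Section 3.3 describes a single-arm study "comparing VFSS and manometry vs VFSS only (the historical control) on feeding outcomes". Section 6.1 defines the comparator: "The controls are those who had VFSS alone with provider recommendations from the same single center".

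For this comparison section 16.1 states: "For PPG vs FOD historical control comparisons, two-sample t-test or ANOVA will be used for the continuous variables and chi-squared" or Fisher's exact tests for categorical variables, with a non-parametric alternative such as Wilcoxon. (PPG is read here as the study group and FOD as the Feeding Outcomes of Dysphagia controls.) Section 16.1 does not name the primary endpoint in this sentence. Because success is binary, chi-squared or Fisher is the implied test.

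Three other places bear on confounding:

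- Section 6.1 has an item on confounders, which opens "Methods to overcome Potential Confounders: It is NICU standard to document in EPIC" and goes on to list routine charting of symptoms, medication, feeding and growth.
- Section 16.1 has one multivariable model for success: "To characterize the association between the disease comorbidities and feeding success, simple and multiple logistic regression analysis will be performed". Study or control group is not named as a term.
- Section 6.1 gives features shared by both groups: "Study and control infants have oral feeding difficulties with symptoms requiring interventions/monitoring", together with a diagnostic need for VFSS and the same centre.

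**The concern.** The groups were not randomised. They differ in period, in parental consent (required for study infants, not for controls) and in who chose the feeding therapy. The last of these is part of the strategy under test; the first two are routes by which prognosis can differ.

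Baseline oral feeding is the clearest risk. Section 3.3 says of the study group: "We will prospectively follow 60 infants who are not fully PO or PO and symptomatic at the time of study". It can therefore include infants who already feed fully by mouth but have symptoms. The endpoint in 6.1 is full oral feeding without symptoms needing intervention, so baseline oral status is plausibly a strong predictor. The document gives no corresponding mix for the controls. Nor does it say whether the controls met the PMA limit, the oral-intake threshold, the full-enteral-feeds and respiratory-support conditions, or the exclusions.

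An unadjusted test cannot separate such differences from the effect of manometry plus parent choice. An imbalance can create an apparent benefit or hide a real one.

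**Working it through.** **Inputs from section 3.3.** Study group n = 60; control success about 60%; target 80%; two-sided alpha 0.05; stated power 90%. The number of controls is not given, so 60, 100 and 200 are assumed below.

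**1. The plan's own figure.** A one-sample test against a fixed 60%, with continuity correction, gives

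power = Φ{[(0.20 − 1/120)·√60 − 1.96·√(0.6·0.4)] / √(0.8·0.2)} = 90.5%.

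Without the correction it is 93.0%. So the stated 90% is reproduced if 60% is a fixed and comparable benchmark. The two-sample test in 16.1 has lower power for a separate reason, namely sampling error in the controls. That shortfall is not confounding and should not be read as such in what follows.

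**2. Effect of a case-mix difference on the planned test.** Rejection probability = ΣΣ Bin(a; 60, p_S)·Bin(b; n_C, 0.60)·1[test rejects], summed over all outcomes. It is two-sided at 0.05, with chi-squared uncorrected.

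| Study-group rate p_S | Test | 60 controls | 100 controls | 200 controls |
|---|---|---|---|---|
| 0.60 | chi-squared | 0.051 | 0.051 | 0.050 |
| 0.65 | chi-squared | 0.087 | 0.095 | 0.105 |
| 0.70 | chi-squared | 0.210 | 0.243 | 0.287 |
| 0.80 | chi-squared | 0.684 | 0.762 | 0.845 |
| 0.60 | Fisher | 0.032 | 0.044 | 0.040 |
| 0.70 | Fisher | 0.155 | 0.227 | 0.262 |

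- *No true effect, imbalance favouring the study group.* A 5-point advantage is the 0.65 row and a 10-point advantage the 0.70 row. False-positive risk goes from about 5% to about 9–10%, or to 21–29%.
- *True 20-point effect, imbalance of 10 points against the study group.* The observed contrast is 70% vs 60%. Chi-squared power falls from 68%, 76% and 84% to 21%, 24% and 29%.

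**3. What a 10-point shift requires, and whether adjustment removes it.** Take one binary baseline factor with success 90% when present and 50% when absent (a 40-point gap). Let its prevalence be 25% in controls and 50% in study infants.

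- Controls: 0.25·0.90 + 0.75·0.50 = 0.60.
- Study: 0.50·0.90 + 0.50·0.50 = 0.70.

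In 20,000 simulated trials per control size with no true effect:

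| | 60 controls | 100 controls | 200 controls |
|---|---|---|---|
| Unadjusted rejection | 0.210 | 0.243 | 0.284 |
| Mantel-Haenszel, stratified on the factor | 0.047 | 0.050 | 0.047 |
| Mean 95% CI half-width, unadjusted (points) | 16.8 | 14.9 | 13.3 |
| Mean 95% CI half-width, stratified (points) | 16.1 | 14.2 | 12.5 |

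In this example, adjusting for the measured factor restores the nominal error rate without widening the interval.

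**4. How many covariates the data can carry.** Expected failures at 80% vs 60% = 0.2·60 + 0.4·n_C = 36, 52 or 92. At an assumed 10 failures per model term that is 3, 5 or 9 terms. Less one for group, this leaves 2, 4 or 8 covariates.

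**The case against.** The strongest reply concerns eligibility. The controls come from the Feeding Outcomes of Dysphagia Study, which has its own protocol, and their selection criteria may be set out there. Section 6.1 is also ambiguous: its population item covers both groups, and the inclusion and exclusion items speak of infants without limiting them to study infants. Against that, the same section attaches the word eligible to the study group only. The defensible statement is that this document does not say the criteria were applied, not that they were ignored. One sentence could settle it.

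Second, 16.1 plans descriptive statistics, and its two-group tests could be used to reveal baseline imbalance. That would show a difference without correcting the effect estimate. The planned logistic model neither includes nor excludes a group term, so it is a natural place for the fix, but as written it does not adjust the study-vs-control effect.

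Third, the illustration is driven by assumptions. A 10-point shift needs a large imbalance in a strong predictor, and a 5-point shift has a modest effect. That is fair, and nothing in the documents indicates which applies.

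Fourth, timing. This version is dated 10/2/20, enrolment was expected to end 7/20, and the control rate has already been reported. Prespecification now can only mean before the primary analysis, planned for 12/20. This limits the remedy but does not remove the need for it.

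**Conclusion.** The concern holds. The test of the primary effectiveness hypothesis is an unadjusted comparison with non-randomised historical controls. Nothing in the plan matches, weights or adjusts for baseline differences, and the document does not state that the 6.1 criteria were applied to the controls. Under an assumed 10-point case-mix difference the error rate of the planned chi-squared test is roughly four to six times nominal. The same difference in the opposite direction removes most of the power. These sizes depend on the assumed control counts and imbalance; the actual imbalance, including its direction, is unknown. The omission of adjustment is clear from the text. The eligibility part is a gap in this document that the control study's own protocol might fill. The remedy is inexpensive, so this is a cheap improvement to the analysis.

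**What to change.** 1. **Controls.** State whether the 6.1 criteria were applied to the FOD controls. If they were not, restrict the controls to records that meet them, apply the 6.1 endpoint definition, and recompute the roughly 60% rate on that set.
2. **Primary estimate.** Estimate the study-vs-control effect on success with a covariate-adjusted analysis: either a logistic model reported as a standardised risk difference with 95% CI, or propensity weighting. Adding group and baseline covariates to the logistic model already in 16.1 is the smallest edit.
3. **Covariates.** Fix a short list, confirmed to be available in both groups, before the primary analysis. Put baseline oral-feeding status and gestational age or PMA first. Add respiratory support and VFSS result only if the number of failures allows. With about 60 controls there is room for two covariates, so choose one of gestational age and PMA, or use penalised or weighted methods.
4. **Reporting.** Give the chi-squared or Fisher result alongside, and do not rest the effectiveness conclusion on it alone. Record which outcome data had been seen when the covariates were chosen.

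**Cost.** SAP wording, one model and chart abstraction for controls. Some controls may be lost to eligibility, and the interval may widen. Adjustment will not remove unmeasured differences such as calendar period or parental willingness to consent, and the report should say so.
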